#### **TRIAL SUMMARY**

Trial Title	Randomised trial of the clinical and cost effectiveness of					
	during in-hospital cardiac arrest (AIRWAYS-3)					
Internal ref. number (or short title)	AIRWAYS-3					
Trial Design	A multi-centre, open-label, pragmatic, individually randomised, parallel group, superiority trial and economic evaluation to determine the clinical and cost effectiveness of a supraglottic airway (SGA) versus tracheal intubation (TI) during in-hospital cardiac arrest (IHCA). The trial will include an internal pilot to confirm feasibility					
Trial Participants	Adult (known or believed to be age >=18) hospital inpatients will be eligible for randomisation if they receive resuscitation following IHCA that requires a 2222 call and advanced airway management					
Planned sample size	4190 participants from centres throughout the UK and internationally					
Treatment Duration	Until return of spontaneous circulation (ROSC) for >20 minutes or resuscitation efforts cease, after which the airway will be managed by the attending team as they feel appropriate					
Follow-up Duration	6-months post IHCA					
Planned Trial Period	1 st January 2022 – 31 st December 2026					
Trial Objectives	
 
(1) Conduct an internal pilot study to confirm the feasibility of the large-scale multi-centre trial
 
(2) Determine the clinical effectiveness of SGA management, for adults with in-hospital cardiac arrest, in terms of survival with a favourable functional outcome and health-related quality of life.
 
(3) Estimate, in an integrated economic evaluation, the cost-effectiveness of SGA compared with TI
 
					
Primary Outcome Measure	Functional status at hospital discharge (or 30 days post- randomisation whichever is shorter) as measured by the modified Rankin Scale (mRS)					
Secondary Outcome Measures	
 
Initial ventilation success
 
Regurgitation/aspiration during resuscitation
 
Return of Spontaneous circulation (ROSC) >20 minutes
 
					

	
 
ICU and hospital length of stay
 
					
	Health-related quality of life at discharge, 3 and					
	6 months)					
	• Survival to hospital discharge, 3 months and 6					
	months					
	
 
Functional status (mRS) at 3 and 6 months
 
					
Economic outcomes	Additional unscheduled care and re-admissions					
	(to 6 months)					
	
 
In-hospital stay utilisation and cost
 
					

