#### 2.3.1 Efficacy

Primary: Modified Rankin Scale (mRS) score assessed at hospital discharge (or at 30 days post-randomisation if the participant remains in hospital).

Secondary:

• Initial ventilation success (visible chest rise with end tidal carbon dioxide monitoring consistent with successful ventilation (where measured) immediately after insertion of a supraglottic airway device or tracheal tube;

• Regurgitation during the resuscitation attempt (stomach contents seen in the patient's pharynx, mouth or nose), and whether this occurred before, during or after advanced airway management;

• Aspiration during the resuscitation attempt (stomach contents seen below the vocal cords, inside a correctly placed tracheal tube or the airway channel of a correctly placed supraglottic airway device), and whether this occurred before, during or after advanced airway management;

- Return of spontaneous circulation (ROSC) for at least 20 minutes;
- Intensive Care Unit length of stay;
- Hospital length of stay;
- Survival to hospital discharge, 3 and 6 months;
- Functional outcome (mRS) score at 3 and 6 months;

• Health-related quality of life at discharge or 30 days (whichever occurs sooner), 3 and 6 months.

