#### 2.8 Randomisation

#### 2.8.1 Randomisation

The randomisation algorithm will be provided by Warwick Clinical Trials Unit (WCTU). A computergenerated randomisation sequence will be created, stratified by hospital site and time of day (8am to 6pm or outside of these hours). Time of day is included as a stratification variable because out-ofhours cardiac arrests tend to have less favourable outcomes (42). Patients will be randomised 1:1 to SGA or TI. Randomisation will take place using a bespoke mobile phone progressive web application (PWA), which will be developed by the programming team at WCTU. The PWA will function asynchronously (off-line) to address any problems with data connectivity that may exist in participating hospitals, and to ensure there is no delay in the randomisation process. If the patient is deemed eligible pressing a single button on screen will immediately display the allocation, and irrevocably enrol the patient. If, due to a technical or other failure, the PWA does not display an allocation within five seconds the patient will be treated according to usual care and the clinical judgement of the cardiac arrest team. If, despite technical failure, the allocation is recorded by the PWA the patient will be included in the study under the "intention to treat" principle, whereas if no allocation is recorded the patient will not be included in the study. Following the IHCA a small additional amount of non-identifiable patient data will be entered to the PWA by the enrolling clinician and automatically uploaded to WCTU. WCTU will then alert the research team at that hospital site for patient identification and follow-up. Preparatory work by the trial team including interviews and simulations has demonstrated that this approach is clinically and technically feasible; it will be tested further during the internal pilot study.

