#### 2.10 Methods to minimise bias

#### 2.10.1 Concealment and blinding

Treatment allocation will be concealed prior to randomisation using a bespoke, computerised randomisation PWA. Screening logs will be assessed to examine reasons why patients have not been enrolled into the study.

The majority of outcomes are objective and will not be influenced by knowledge of treatment allocation. It will not be possible to blind clinical team members to treatment allocation following randomisation. Blinding of the wider clinical team and site research team will be limited as cardiac arrest team members may document treatment allocation in the patient's medical record. Patients will be blinded because they are in cardiac arrest and unconscious when the allocated airway management occurs. Site teams will be encouraged to maintain blinding by not informing patients or their relatives of their treatment allocation, unless the participant or consultee states a specific wish to be informed.

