#### 6.2.3.3 Secondary outcome analysis

Outcome	Source of Data	Justification				

Initial ventilation success (visible chest rise and evidence of end tidal carbon dioxide on capnography)	App data entry following IHCA	Primary goal of advanced airway management is to deliver effective ventilation
Regurgitation (stomach contents visible in the mouth or nose) or aspiration (stomach contents visible below the vocal cords or inside a correctly placed tracheal tube or airway channel of a supraglottic airway device)	App data entry following IHCA	Different advanced airway management techniques may be associated with different risks of regurgitation and/or aspiration
Return of spontaneous circulation (ROSC) > 20 minutes	NCAA and/or data collection by research staff at participating sites	Short-term outcome following cardiac arrest
Critical care length of stay (number of days from randomisation	NCAA and/or data collection by research staff at participating sites, HES	Measure of health service use, Required for health economic analysis
Hospital length of stay (number of days from randomisation)	NCAA and/or data collection by research staff at participating sites, HES	Measure of health service use, Required for health economic analysis
Survival to hospital discharge, 3- months and 6-months	NCAA and/or data collection by research staff at participating sites, HES	Included in the cardiac arrest core outcome set
mRS score at 3-months and 6- months	Postal CRF/eCRF/CRF completed by telephone	Included in the cardiac arrest core outcome set; patient-centred outcome
Health-related quality of life (EQ- 5D-5L) at 3-months and 6-months	Postal CRF/eCRF/CRF completed by telephone	Included in the cardiac arrest core outcome set; required for health economic analysis; patient- centred outcome
In-hospital stay utilization and costs	HES	Required for health economic analysis
Additional unscheduled care and readmission (to 6 months)	HES	Required for health economic analysis
Adverse events/ serious adverse events	CRF (in-hospital patient notes)	All serious adverse events and adverse events that are related to the intervention will be reported, in line with Warwick CTU operating procedures.

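### The aspiration outcome is scored by a device-dependent criterion, and the protocol's sections define it differently, so a difference in aspiration alone cannot be read as a device effect

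*Protocol*

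**What the plan says.** Section 2.3.1 lists regurgitation and aspiration as separate secondary outcomes, each with a record of its timing relative to advanced airway management. Regurgitation is "stomach contents seen in the patient's pharynx, mouth or nose". Aspiration is "stomach contents seen below the vocal cords, inside a correctly placed tracheal tube or the airway channel of a correctly placed supraglottic airway device".

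Section 6.2.3.3 puts both in a single row joined by *or*. Regurgitation there is "stomach contents visible in the mouth or nose", without the pharynx. Aspiration is "stomach contents visible below the vocal cords or inside a correctly placed tracheal tube or airway channel of a supraglottic airway device", which attaches the correct-placement condition explicitly only to the tracheal tube. The stated reason for the outcome is that the techniques may carry different risks of these events. The trial summary has one item, "Regurgitation/aspiration during resuscitation".

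The source is "App data entry following IHCA". Section 2.8.1 says "non-identifiable patient data will be entered to the PWA by the enrolling clinician", and section 2.10.1 says "It will not be possible to blind clinical team members to treatment allocation following randomisation". Section 6.2.1 analyses categorical secondary outcomes by mixed-effects logistic regression and reports odds ratios with 95% confidence intervals.

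**The concern.** The outcome exists to compare two devices, but one of its criteria is tied to which device is in place. An SGA channel opens above the glottis, as the device's name implies, and a tracheal tube lumen opens below the cords. Contents that have not passed the cords can meet the aspiration criterion through an SGA. Contents at the same level around a tracheal tube cannot. An odds ratio for aspiration then mixes any device effect with the scoring rule.

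The protocol neither mentions this nor adjusts for it. The safety data will not supply a substitute comparison, because section 4.2 lists aspiration pneumonia among the anticipated events that are not reported as SAEs.

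A second problem is the disagreement between sections. Whether there is one outcome or two, and whether contents in the pharynx count, changes which patients are events.

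**Working it through.** The protocol states no aspiration or regurgitation rate, so there is no figure of its own to reproduce. The check has two parts.

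**1. The definitions applied to the same records**

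| Record | 2.3.1 regurgitation | 2.3.1 aspiration | 6.2.3.3 combined row |
|---|---|---|---|
| A. SGA in place; contents in pharynx and SGA channel, none below cords, none in mouth or nose | yes | yes | yes |
| B. Tracheal tube in place; contents in pharynx at the same level, none in tube, mouth or nose | yes | no | no |
| C. SGA in place; contents below cords, none showing in channel, pharynx, mouth or nose, cords not viewed | no | no | no |
| D. Tracheal tube in place; contents below cords, seen in tube or at laryngoscopy | only if also seen above cords | yes | yes |

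A and B have the same soiling but different aspiration scores under both sections. Under 6.2.3.3, B is not an event at all, so combining the two events with that section's wording does not remove the difference. A combined outcome using the 2.3.1 wording scores A and B alike. C and D show a second difference, in detection, which acts in the opposite direction.

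**2. Can a net bias be derived?**

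All inputs are assumptions, with no true device effect and with every patient managed with the allocated device:

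- p = share of patients with contents reaching the pharynx
- f = share of those in whom contents pass the cords
- g = share of supraglottic-only soiling that shows in the SGA channel
- d = share of below-cord contents detected in SGA patients (detection with a tracheal tube is taken as complete)

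Scored aspiration is:

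- TI = p × f
- SGA = p × [f × d + (1 − f) × g]
- The two are equal when d = 1 − (1 − f) × g / f

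With p = 10%, f = 50% and g = 25%, TI = 0.10 × 0.50 = 5.0%. For SGA:

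- d = 100%: 5.0% + 1.25% = 6.25%, OR = (0.0625/0.9375)/(0.05/0.95) = 1.27
- d = 75%: 3.75% + 1.25% = 5.0%, OR = 1.0
- d = 50%: 2.5% + 1.25% = 3.75%, OR = (0.0375/0.9625)/(0.05/0.95) = 0.74

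Break-even detection for other assumed rates:

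| p | p × f | g | Break-even d |
|---|---|---|---|
| 20% | 10% | 10% | 90% |
| 20% | 5% | 10% | 70% |
| 30% | 10% | 25% | 50% |
| 20% | 5% | 25% | 25% |

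The protocol fixes none of p, f, g or d. The odds ratio can fall on either side of 1 with no true difference between the devices.

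**The case against.** **The criterion can be defended.** Inside a correctly placed tracheal tube and inside the channel of a correctly placed SGA are both the ventilation path of a working device. The rule may be a deliberate functional parallel. It also gives SGA patients, whose cords are usually not seen, a way to be scored; a rule restricted to contents below the cords would leave little means of detection. This stands as a reason not to delete the channel criterion. It does not put the two criteria at the same anatomical level, so the comparison still needs a caveat.

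**Scoring follows the device in place, not the allocation.** Section 2.5 allows a temporary SGA before randomisation. Section 2.9.1 allows the other technique after two failed attempts. Section 2.8.2 retains patients who never receive the allocated device. The channel criterion can therefore be met in the TI arm, and the cords can be viewed in the SGA arm. This stands, and it dilutes the contrast. It does not remove it, because allocation is meant to determine the device.

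**A reader might infer a false harm signal against the SGA, with a calculable false-positive rate.** The documents do not support that. Such a calculation needs assumed rates and complete detection of below-cord contents in SGA patients. Once detection is allowed to be incomplete, the sign can reverse.

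**A reader might also conclude that aspiration should no longer be formally compared.** That does not follow either. Aspiration is the more consequential event, and a caveated comparison keeps the information.

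**Conclusion.** The point holds as a matter of definition. In both 2.3.1 and 6.2.3.3 the aspiration criterion depends on the device in place. Under 6.2.3.3, contents confined to the pharynx count through an SGA channel but not at all in an intubated patient. The trial summary and 6.2.3.3 also conflict with 2.3.1 on the number of outcomes, and 6.2.3.3 conflicts with 2.3.1 on the pharynx. These conclusions rest on the wording and on the position of the two airways relative to the cords, not on any assumed rate.

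The net direction and size of any bias are unknown, and no false-positive rate can be stated. The illustrative odds ratios show only that the sign is not determined. One secondary outcome is affected. The primary outcome and the sample size of 4,190 are untouched.

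**What to change.** 1. Reconcile the trial summary, 2.3.1 and 6.2.3.3 to one set of definitions that keeps pharynx in regurgitation, and state whether regurgitation and aspiration are one outcome or two.
2. Add a between-arm comparison of any regurgitation or aspiration: stomach contents seen in the pharynx, mouth or nose, below the vocal cords, or inside the airway device. An event then counts however it is labelled.
3. Keep the aspiration comparison. State beside it that the criterion differs by device and that laryngoscopy changes detection, so a difference in aspiration alone is not read as a device effect without the composite.

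The cost is wording in three places, and in the SAP where it repeats them. No new data are needed if the app records the 2.3.1 items, since the composite is formed from those entries. The drawbacks are that the composite pools events of different severity, and that some detection difference remains because laryngoscopy gives a better view of the pharynx and cords.

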#### 2.3.2 Safety

Adverse events/serious adverse events described in section 4.

#### 2.3.3 Health Economic

Additional unscheduled care and re-admissions (to 6 months). Resource use will include intervention, hospital (ICU, HDU and ward days) and community costs (primary care and social care costs).

#### 2.4 Eligibility criteria

Patients are eligible to be included in the trial if they meet the following criteria:

#### 2.4.1 Inclusion criteria

• Adult (known or believed to be age >=18)

• In-hospital cardiac arrest, attended by the hospital cardiac arrest team in response to a cardiac arrest call (2222 or equivalent), and when a clinician permitted to undertake both tracheal intubation and supraglottic airway placement (so that either intervention can be delivered) is present

• Undergoing resuscitation and requiring advanced airway management in the opinion of the trained clinician responsible for randomisation

#### 2.4.2 Exclusion criteria

- Patients who have a cardiac arrest outside hospital and who are transported to the hospital in ongoing cardiac arrest
- People who are not a hospital inpatient (e.g. visitor, relative, staff or outpatient)
- Patients who are already tracheally intubated at the time of eligibility assessment
- Patients known to be pregnant
- Patients with a functioning tracheostomy

#### 2.5 Participant identification / Screening

In study hospitals, the cardiac arrest team will be activated by clinical staff via the hospital switchboard as is usual practice. On arrival at the event, the cardiac arrest team will deliver care in accordance with Resuscitation Council UK guidelines or as per locally agreed guidelines for international sites. A member of the in-hospital cardiac arrest team who is trained in trial procedures and Good Clinical Practice (GCP), and who has been authorised to enrol patients on the delegation log, will screen the patient to assess their eligibility. This will usually be the member of the in-hospital cardiac arrest team who is designated to manage the patient's airway, however another member of the team may enrol the patient providing they are trained and authorised to do so, and a clinician permitted to undertake both tracheal intubation and supraglottic airway placement is present to manage the patient's airway. Our recent national survey shows that this is most commonly a doctor who is training to become a consultant in either anaesthesia or intensive care (9). This approach will enable study recruitment to be undertaken on a 24/7 basis. Before a clinician permitted to undertake both tracheal intubation and supraglottic airway placement arrives, and randomisation can proceed, the airway will be managed according to usual practice in that hospital site. This will usually be bagmask ventilation, but may be the temporary placement of a SGA device in some centres.

A record of the event will be made in the study screening log subsequently. If a patient is identified as being eligible, then the patient will proceed to randomisation.

# 2.6 Site Staff Training

Educational and training materials will be developed to standardise the processes for training in study procedures, trial enrolment, treatment delivery, data recording and proportionate GCP. Materials will be developed to support study staff at the site initiation visit, which may be conducted virtually. In addition to this, the AIRWAYS-3 trial team will: provide advice and support to site PIs; provide instructional material to all trial sites; provide detailed instructions on protocol and a training manual which may be delivered in video and online formats.

#### 2.7 Consent Procedures

#### 2.7.1 Research Without Prior Consent and the Health Research Authority Framework

The time-critical nature of the emergency and patient status (immediately unconscious due to cardiac arrest) means it will not be feasible to seek informed consent from the patient or a consultee before trial enrolment. The trial will fall under the legislative framework of the Mental Capacity Act 2005 in the UK. Approval from an appropriately "flagged" research ethics committee to enrol patients without prior consent will be sought. This approach is permitted under the Mental Capacity Act 2005 for life-threatening conditions such as cardiac arrest where there is no practical alternative. This protocol has been prepared for recruitment in England and Wales, in consideration of the legal requirements in these nations. Should recruitment occur in Scotland or Northern Ireland it will be updated accordingly, taking account of the differences in legislation that exist in the devolved nations. International sites will seek approvals according to their local policies and practices.

#### 2.7.2 Participants who survive

For patients who survive, the hospital research team will provide trial information and seek patient consent for ongoing participation. In the event the patient lacks capacity an appropriate personal or professional consultee will be approached instead. A personal consultee is preferred, and a professional consultee will only be approached if no personal consultee can be identified before the patient is discharged from hospital, or a potential personal consultee declines to take on this role. NHS interpreter services will be used, as and when required, to support the provision of information to participants. Experience in previous trials is that this approach is well received by patients and families who appreciate the research team taking the time to explain the trial to them, and this has led to high levels of consent to continue. However, to ensure 100% ascertainment of the primary outcome this will be collected for all enrolled patients (those who do and do not survive) from routinely available data collected locally and by the National Cardiac Arrest Audit with the prior permission of the Health Research Authority Confidentiality Advisory Group (CAG).

When an approach is made, the trial intervention will have been completed. The researcher will inform the participant (or their consultee) of their enrolment and explain that the focus of the consent process relates to ongoing participation; namely the collection of routinely available data and patient-reported outcome measures through questionnaires. Patients will be offered three consent options:

- a. No further participation
- b. Collection of routine data from the patient's health records, but no further contact from the study team and no requests to complete follow-up questionnaires
- c. Collection of routine data from the patient's health records and the completion of follow-up questionnaires

To avoid the risk of significant bias, primary outcome data will be processed without the patient's consent, and there is no option to withdraw from the trial completely. This is considered further in Section 7.3 (Confidentiality Advisory Group (CAG) approval).

#### 2.7.2.1 Participants with mental capacity

If the participant regains mental capacity a researcher will approach them at an appropriate time, working in close liaison with the clinical staff who are caring for the patient, to discuss ongoing study participation. The researcher will provide information about the trial and the participant information sheet. The participant will be given adequate time to review the information sheet and an opportunity to ask questions. This may require several discussions over a period of time. The participant's consent to the collection of routine data and patient-reported outcome measures will be recorded on a signed consent form, counter-signed by the staff member taking consent. The consent form may be signed physically, or where the participant is unable to sign the form, either in wet ink or electronically, verbal consent may be recorded by the staff member and witnessed by one other person. Electronic consent will be taken through Qualtrics to ensure a clear audit trail and security.

